7.10 Data Monitoring Committee (DMC)

The DMC will consist of independent experts with relevant clinical research, and statistical experience. The DMC will meet after the first 624 patients have been recruited and regularly every 6 months thereafter. Confidential reports containing recruitment, protocol compliance, safety data and interim assessments of outcomes will be reviewed by the DMC. The DMC will advise the TSC as to whether there is evidence or reason why the trial should be amended or terminated. In the unlikely event that the DMC recommends an early termination of the trial, whether due to safety concerns or for other reasons, a recommendation will be made immediately.

DMC meetings will also be attended by the Chief Investigator and Trial Manager (for non-confidential parts of the meeting) and the trial statistician.

The full remit and responsibilities of the DMC will be documented in the Committee Charter which will be signed by all members.

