----------	--------------------------	----

TRIAL SUMMARY

Trial Title	Randomised controlled trial of the clinical and cost-effectiveness of cervical spine immobilisation following blunt trauma (SIS trial)	
Internal ref. number (or short title)	SIS trial	
Trial Design	A multi-centre, open-label, pragmatic, pre-hospital, non-inferiority randomised controlled trial with health economic evaluation to determine the effectiveness of immobilisation regimes involving movement minimisation and triple immobilisation (current NHS practice) in patients with cervical spine (c-spine) injury recruited in a pre-hospital setting.	
Trial Participants	Patients (any age) in a pre-hospital setting with potential or suspected c-spine injury.	
Planned sample size	8,316 participants	
Treatment Duration	The interventions will be administered at initial pre-hospital clinical assessment and will remain in place for as long as is clinically required.	
Follow-up Duration	Participants will be followed-up for 180 days	
Planned Trial Period	01 November 2022 – September 2025 with an internal pilot phase 01 November 2022 – 30 April 2023	
	Objectives	Outcome Measures
Primary	To determine whether movement minimisation is deemed non-inferior compared to triple immobilisation in relation to functional outcome at hospital discharge.	Functional Independence Measure (Motor) score
Secondary	To determine the effects of immobilisation techniques on clinical, patient-centred and economic outcomes pre-hospital, in hospital and at 180 days post-randomisation.	Need for pre-hospital analgesia Neurological change (randomisation to hospital discharge) Mortality (30, 90 and 180 days) Length of stay in critical care and hospital Further intervention for c-spine injury Costs and resource utilisation Adverse events
Quality of Life	To determine the effects of immobilisation techniques on patient-centred outcomes pre-hospital, in hospital and at 180 days post-randomisation.	Quality of life measurements (EQ-5D-5L/EQ-5D-Y)

LIST OF ABBREVIATIONS/GLOSSARY

Abbreviation	Explanation
AE	Adverse Event
ASIA	American Spinal Injury Association Impairment Scale
CI	Chief Investigator
CONSORT	Consolidated Standards of Reporting Trials
CRF	Case Report Form
C-spine	Cervical spine
CTU	Clinical Trials Unit
DMC	Data Monitoring Committee
EQ-5D-5L	EuroQol five-domain health utility measure (five level)
EQ-5D-Y	EuroQol five-domain health utility measure (Youth)
FIM	Functional Independence Measurement
GCP	Good Clinical Practice

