2.12 Pilot phase

The main trial will be preceded by an internal pilot phase of 6 months duration. This will follow the same processes as the main trial, and all patients recruited during the pilot phase will be included in the final analysis. The pilot will take place in 2 ambulance services (and associated air ambulance services where appropriate) to confirm recruitment rates, protocol compliance and data collection, and will aim to recruit 624 patients. In particular, we will audit: (a) screening data; (b) recruitment; (c) reasons for exclusion; (d) protocol adherence, crossovers and fidelity to the intervention; (e) implementation of the training and protocol into practice, using screening logs, case report forms (CRFs) and virtual site visits.

Trial progression criteria will be:

	Red	Amber	Green
RECRUITMENT			
% Threshold	<30%	30-74%	75-100%
Total number of participants recruited	<187	187 - 467	468 - 624

Success criteria for recruitment will be

- (a) 75-100% recruitment: progress to main trial following a review of screening logs and protocol. Any barriers for recruitment will be addressed;
- (b) 30-75% recruitment: progress to main trial with additional sites being recruited as well as a screening log and protocol review;
- (c) less than 30% recruitment: the decision to progress will be made by the Trial Steering Committee in association with the HTA secretariat.

On reaching the pre-defined success criteria, the internal pilot will run seamlessly into the main trial. The pilot study results will be reported in accordance with the CONSORT guideline for pilot studies¹⁸.

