6.4 Interim analysis and criteria for the premature termination of the trial

The timing and frequency of the interim analyses will be discussed and agreed with the Data Monitoring Committee members. It is anticipated that no more than one formal interim analysis will take place during the course of the study. The statistical stopping criteria will be formalised using the O'Brien and Fleming stopping rules²⁷. In making a decision to terminate the clinical trial, the Data Monitoring Committee will use the statistical evidence as guidance to their decision making and will be also presented with a 95% confidence interval of the treatment difference.

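### The first DMC meeting is scheduled only by reaching 624 recruits, the full pilot target, so at any lower recruitment the trial can enter its main phase before any scheduled independent comparison of safety by arm

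*Protocol*

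**What the plan says.** Protocol section 7.10 gives the DMC's whole schedule in one sentence: "The DMC will meet after the first 624 patients have been recruited", and then at six-month intervals. It sets no calendar date and no link to the pilot decision. The committee's full remit is left to a charter.

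The pilot, by contrast, is fixed by calendar. Section 2.12 states: "The main trial will be preceded by an internal pilot phase of 6 months duration". The Trial Summary gives the dates: "internal pilot phase 01 November 2022 – 30 April 2023". The pilot "will aim to recruit 624 patients", the same figure as the DMC trigger.

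The red, amber and green counts in section 2.12 are "<187 187 - 467 468 - 624". The amber action is: "30-75% recruitment: progress to main trial with additional sites being recruited as well as a screening log and protocol review". Green also leads on to the main trial after a review of screening logs and protocol. In the red band the Trial Steering Committee decides, together with the HTA secretariat. The pilot then runs into the main trial without a pause. No progression criterion asks for a DMC meeting or a review of safety data.

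Sections 4.4.3 and 4.5 make the DMC the body that sees serious adverse events by arm and unblinded safety data. It does so at its regular meetings, or more often if its Chair asks.

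**The concern.** One milestone is set by the calendar (the end of the pilot) and the other by a count (the first DMC meeting). They coincide only if the pilot recruits its full target on time. If it does not, the trial moves on, and in the amber band opens further sites, before the committee that compares the arms has been due to meet. Because the six-monthly cycle hangs on the first meeting, every later meeting slips with it.

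The experimental arm leaves out the collar in patients whose cervical spine has not been cleared, and participants are enrolled before consent. Section 4.5 itself says that the DMC looks for patterns that single cases would not reveal. At stake is whether a first look of that kind is assured by a known date.

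**Working it through.** **Inputs**
- First DMC meeting: 624 recruits (section 7.10)
- Pilot: 6 months, target 624 (section 2.12)
- Bands: amber 187 to 467, green 468 to 624 (section 2.12)
- Planned size: 8,316 (section 6.1)

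**Reproducing the plan's bands.** 0.30 × 624 = 187.2 and 0.75 × 624 = 468. In reverse, 187/624 = 30.0%, 467/624 = 74.8% and 468/624 = 75.0%. The stated counts are reproduced. The table labels amber as 30-74% and the text as 30-75%; I use the counts, so this makes no difference here.

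**Order of events.** Every amber count, and every green count from 468 to 623, is below 624. At month 6 none of these has reached the DMC trigger.

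**Length of the lag.** Let r be the number recruited by month 6.
- Pilot rate = r/6 per month
- Shortfall = 624 − r
- Lag at unchanged rate = (624 − r) ÷ (r/6)
- Lag if added sites double the rate = (624 − r) ÷ (2r/6)
- Lag if the rate rises to the pilot target, 624/6 = 104 per month = (624 − r) ÷ 104

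| Recruited by month 6 | Rate per month | Shortfall | Lag, same rate | Lag, doubled rate | Lag, 104 per month |
|---|---|---|---|---|---|
| 187 (lowest amber) | 31.2 | 437 | 14.0 months | 7.0 | 4.2 |
| 312 (50% of target) | 52.0 | 312 | 6.0 | 3.0 | 3.0 |
| 467 (highest amber) | 77.8 | 157 | 2.0 | 1.0 | 1.5 |
| 468 (lowest green) | 78.0 | 156 | 2.0 | 1.0 | 1.5 |
| 624 (full target) | 104.0 | 0 | 0 | 0 | 0 |

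Counted from the start of recruitment at an unchanged rate, the first meeting falls at month 20 (lowest amber), month 12 (half of target) or month 8 (lowest green).

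**Exposure.** 624/8,316 = 7.5% of the planned sample, about 312 per arm. This does not depend on the speed of recruitment.

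**What covers the gap.** Set beside the DMC's role, the other safeguards are:
- Review of each serious adverse event on receipt by the Chief or Co-Chief Investigator or a delegate (section 4.4.3), with an independent clinical reviewer as an alternative (section 4.5). This is case by case.
- Reporting of related and unexpected events to the ethics committee and sponsor within 15 days (section 4.4.3). This too is case by case.
- Periodic safety review by the Steering Committee (section 4.5). The text does not say that it sees unblinded data.
- The DMC Chair's power to ask for by-arm reports of serious adverse events more often (section 4.4.3). This is discretionary. It also covers only what is reported as serious: section 4.3 limits that to events possibly related to trial treatment, and section 4.3.1 exempts skin breakdown, pneumonia and intracranial hypertension, which largely match the safety outcomes in section 2.3.2.

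**The case against.** The best defence is that a count trigger controls the right quantity. It caps exposure before review at about 624 participants, however slow recruitment is; a longer wait only means fewer patients per month. The pilot decision is also a test of feasibility, with recruitment counts as its criteria, so passing it before a DMC meeting contradicts nothing in the protocol. Both points stand. They make this an improvement to the design rather than an error, but they do not supply a date for the first by-arm review.

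Three stronger readings are tempting and are not supported:
- **That independent oversight is absent before 624.** The safeguards listed above operate from the first patient, the Steering Committee has an independent Chair (section 7.9), and the ethics committee can stop the trial (section 2.13). What is missing is a guaranteed, scheduled comparison of the arms.
- **That the delay is 20 months.** That is the bottom edge of amber with the rate unchanged, whereas amber requires sites to be added.
- **That the DMC must settle the interim analysis before it has met.** Section 6.4 says "The timing and frequency of the interim analyses will be discussed and agreed with the Data Monitoring Committee members", but sets no deadline. No more than one formal interim is anticipated, and nothing places it before 624 recruits. There is no conflict of order.

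The charter is not shown and may set an earlier meeting.

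**Conclusion.** The point holds in a limited form. As section 7.10 is written, only full recruitment of 624 by month 6 brings the first scheduled DMC meeting level with the pilot decision. Anywhere in the amber band, and in the green band short of 624, the trial progresses first. For amber the lag after the pilot is about 2 to 14 months at an unchanged rate, about 1 to 7 months at a doubled rate, and about 1.5 to 4.2 months at 104 per month. The doubled and target rates are assumptions, since the protocol does not say what added sites would yield. All three scenarios take a steady rate within each period.

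The order of events is certain from the protocol's own figures. Its practical weight is moderate, because exposure is capped at about 7.5% of the sample and other safety channels run throughout.

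**What to change.** Reword section 7.10 so that the DMC first meets at the earlier of 624 participants randomised or a fixed date near the end of the six-month pilot, and every six months after that. A data cut at month 5, for example, would leave time for a report. State that the DMC's advice is to be available before the pilot progression decision and before additional sites open. Do not tie the wording to a Steering Committee decision, because section 2.12 gives that committee the decision only in the red band. The charter should be brought into line.

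The cost is at most one earlier report and meeting, on a smaller first dataset. At 187 recruits it would hold about 93 per arm (187/2); a month-5 cut at the same rate would hold about 78 per arm (5 × 31.2 = 156; 156/2 = 78). That is thin for a formal comparison, but enough for a first look at safety, compliance and data flow. No efficacy look is needed. If recruitment runs at or near target, the change moves the first meeting by a few weeks at most.

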7.11 Essential Documentation

A Trial Master File will be set up according to the relevant WCTU SOPs and held securely at the coordinating centre.

The coordinating centre will provide Investigator Site Files to all recruiting centres involved in the trial.

7.12 Financial Support

The trial is funded by the National Institute for Health Research (NIHR) HTA programme reference NIHR131430. The views expressed are those of the author(s) and not necessarily those of the NIHR or the Department of Health and Social Care.

8. MONITORING, AUDIT AND INSPECTION

A Trial Monitoring Plan will be developed by the trial team and approved by the CI, a member of the QA team and the Sponsor. A risk based proportionate approach will be outlined in the monitoring plan to facilitate remote and off-site monitoring if required.

9. PATIENT AND PUBLIC INVOLVEMENT (PPI)

Two groups, ASPIRE (Association for Spinal Injury Research, Rehabilitation & Reintegration) and the Imperial PPI group were instrumental in reviewing and amending the proposal at the design phase and helped identify the FIM as the appropriate outcome measure for the trial. Additionally,

consideration around the ethics of the trial (for example, consent waiver on scene) but subsequent consent when in hospital and the processes around this have shaped the trial to date and will continue to do so.

ASPIRE is a charity which supports around 50,000 people living with spinal injury in the UK. They will support the trial to ensure there is clear evidence in support of the most effective pre-hospital patient care, ensuring the best possible outcome for the patient.

The Imperial PPI group comprises spine and head injured patients and have experienced spinal immobilisation. The head injured patients experienced this when it was subsequently found to be unnecessary and therefore provide an important balance in the group.

The insight that service user representatives can offer from the patients' perspective complements the clinical expertise and specialist knowledge of the research team and will ensure that the trial maintains an approach which is centered on patients and their needs.

The PPI members will have input on the interpretation of the data at the end of the trial which will shape subsequent publications and, ultimately, guidelines. The PPI team will also be involved in the write-up of the outputs from this research and the dissemination of the findings.

10. DISSEMINATION AND PUBLICATION

The results of the trial will be reported first to trial collaborators. The main report will be drafted by the trial coordinating team, and the final version will be agreed by the Trial Steering Committee before submission for publication, on behalf of the collaboration.

The success of the trial depends on the collaboration of doctors, nurses and researchers from across the UK. Equal credit will be given to those who have wholeheartedly collaborated in the trial. The trial will be reported in accordance with the Consolidated Standards of Reporting Trials (CONSORT) guidelines (www.consort-statement.org).

A communication strategy will be developed that involves all partners. The strategy will include identifying key stakeholders, messaging, channels for communication, coverage and frequency and potential risks and sensitive issues associated with the research. Dissemination activities will start as soon as we are permitted to share information about the trial. Audiences include patients and the public, clinicians (doctors, nurses and others), researchers and academic experts, policy makers (NHS England), national and international guideline groups, particularly those related to resuscitation. A series of outputs will maximise the impact of this research including conference presentations and other dissemination events.

